15.1 Data Collection

15.1.1 Data Management Overview

Data management will be handled by the MSMC Stroke Clinical Research Group, which is housed in the Department of Neurological Surgery at the Mt. Sinai Medical Center (MSMC). All activities will be conducted in coordination with the study PI, the sites, and the TOC. The data validation procedure will be implemented in two stages. First, the automated data checks will flag items that fail a rule, and the rule violation message will appear on the data entry screen at the time of data entry. The Study Coordinator at a site will see these rule violations and will be required to provide a response. His/her choices are to: (1) correct the entry immediately; (2) correct the entry at a later time; or (3) if the entered data are confirmed to be correct, dismiss the rule by checking that option provided by the REDCap system. Any changes made to the data will have a full audit trail. Second, for some checks that are more complicated, additional consistency checks will be run periodically after data entry occurs at the site. All data items that fail the programmed consistency checks will be queried via the data clarification request (DCR) process initiated by the MSMC data managers. Site Monitors will also be able to generate DCRs when discrepancies are found during source document verification. The DCRs will be generated, communicated to the sites, and resolved on the secure study website.

In addition to the study database, MSMC will provide the site staff password protected access to a standard set of web-enabled tools, including subject visit calendar, subject accrual status, case report form completion status, and outstanding DCR status pertaining to their respective sites.

15.1.2 Data Acquisition and Central Study Database

The entire study will be conducted using an electronic data acquisition method where all clinical data on enrolled subjects will be data entered (single-keyed) by the site personnel into a web-based data management system, REDCap. In order to provide user-friendly and easy-to-navigate interfaces, the REDCap data capture screens are designed based upon individual CRFs. Additionally, REDCap provides 24/7 technical support should difficulties arise. Prior to study start, the system is validated to ensure the data entry screens mirror the CRFs and that the pre-programmed data rules appropriately detect incorrect data. The data will be managed after data entry via data queries

from the MSMC.

The latest version of each CRF and source documents will be available as a PDF file on the REDCap website for use by study personnel. This process facilitates version control of these study related documents, particularly since documents may evolve over the course of the study.

This user friendly web-based database system, developed and validated by the MSMC, will be used for subject randomization, data entry, data validation, project progress monitoring, subject tracking, user customizable report generation and secure data transfer.

15.3 Reporting Module

The REDCap system also has a real-time reporting component that allows authorized users to view protocol specific reports as data listings and in a summary format, overall and by site, at any time during the study via the password protected system. The Reporting Module is developed based on input from the TOC and includes reports on enrollment, SAEs, CRF processing, and subject progress. The reports are presented in a manner that protects the integrity of the study (e.g., blinded).

MSMC will provide the TOC and authorized study personnel access to a standard set of web-enabled tools within REDCap. These tools allow the authorized research personnel to receive regular updates on accrual status and CRF status of enrolled subjects. Examples of available reports include subject enrollment logs, basic subject demographics, CRF completion rate and number of data queries outstanding and resolved. Like all reports generated on the system, data reported are in real time.

15.4 Security, Privacy, and Confidentiality

The MSMC employs several layers of data protection to ensure data security.

The first part of security is physical protection of the hardware systems employed by the MSMC. The facility housing the MSMC hardware is protected 24/7 by multiple layers of security. By limiting access, ensuring only authorized personnel have access, and tracking all entry, we can ensure this risk is minimal. All communication with the web server and client is encrypted. To help protect and secure the data stored in REDCap's back end database, the software application employs various methods to protect against malicious users who may attempt to identify and exploit any security vulnerabilities in the system. In REDCap, all incoming data gets intentionally filtered, sanitized, and escaped. Server environment variables that are vulnerable to forgery by end-users are also checked and sanitized. To specifically protect against Cross-Site Request Forgery (CSRF), which is another method of attack, REDCap utilizes a "nonce" (a secret, user-specific token) on every web form used in the application. The nonce is generated as a unique value for each new REDCap session

To maintain electronic records in the database as adequate and accurate, REDCap system tracks all changes made to any study patient-related and dynamically managed electronic records. REDCap has a built-in audit trail that automatically logs all user activity and logs all pages viewed by every user, including contextual information (e.g. the project or record being accessed). The logging record can itself be viewed within a project by users that have been given privileges to view the Logging page. The Logging page allows such users to view or export the entire audit trail for that project, and also to filter the audit trail in various ways based upon the type of activity and/or user. This audit-trail information is created with a computer generated time-stamp and the user name in chronological order, when the original data is modified or deleted.

16. Adverse Events

Adverse events (AEs) may occur at any time after randomization. Pre-existing conditions (existing prior to randomization) will be documented in the subject's medical record as part of prior medical history but will not count against either study procedure unless there is a worsening of the condition during the study. Adverse events (serious and non-serious) will be documented on an Adverse Event CRF. Non-serious adverse events will be recorded from randomization through hospital discharge or 7 days whichever is earlier. Serious adverse events will be recorded from randomization through the end of study (i.e., 180 day follow-up).

Investigators will record characteristics of each adverse event on an Adverse Event CRF. Each adverse event will be judged by the Investigator as to its level of relatedness to the investigational devices and investigational procedure. In addition, the Investigator will identify the date of onset, severity and duration. Severity will be judged using the scale noted in Table 10. All adverse events will be monitored until they are adequately resolved or explained or until the subject reaches the end of the study.

Table 10. Definition of event severity for judgment by Investigator.

Term	Definition
Mild	Patient is aware of a sign or symptom, but that sign or symptom does not interfere with normal activity or symptom is both transient and resolved
Moderate	Symptoms interfere with the subject's usual activity or symptoms require treatment
Severe	Symptom(s) cause either severe discomfort or have a significant impact of the subject's usual activity and symptoms require treatment

16.1 Serious Adverse Events

An adverse event is considered serious if it is life-threatening, prolongs hospitalization, requires a re-hospitalization, inpatient hospitalization, results in significant disability, or leads to death. Additionally, an important medical event that may not result in death, be life-threatening, or require hospitalization may be considered a serious adverse event when, based upon appropriate medical judgment, the event may jeopardize the subject and may require medical or surgical intervention to prevent one of the outcomes listed in this definition. Examples of such medical events include (but are not limited to): allergic bronchospasm requiring intensive treatment in an emergency room or at home; blood dyscrasias or convulsions that do not result in inpatient hospitalization; or, the development of drug dependency or drug abuse. Serious adverse events should not be reported for hospitalization or prolonged hospitalization in the following scenarios: for a diagnostic or elective surgical procedure related to a pre-existing condition; to allow for an efficacy measure for the study; or, for a planned surgical procedure that was not the result of a condition worsening due to participation in the study.

An assessment should be made regarding the seriousness, severity and relationship to the investigational devices and investigational procedure. The following factors should be considered when evaluating causality of adverse events: 1) the temporal sequence from the study procedure; 2) patient's response after discontinuation or re-introduction; and, 3) severity of the event. The investigators, on the basis of their clinical judgment and guided by the following definitions, should determine the relationship of an adverse event to the administration of the investigational device, and/or study procedure(s) as: definitely related, i.e. following in a reasonable temporal sequence, known to be a complication, and having no other explanation; probably related, i.e. following in a reasonable temporal sequence and not reasonably explained by the patient's clinical state or other therapies; possibly related, i.e. could have been explained by other therapies or patient's clinical state; or not related.

16.2 Reporting and Review of Adverse Events

To provide for consistent reporting of adverse events, serious and non-serious adverse events will be recorded on the Adverse Event CRF. Non-serious adverse events will be recorded from randomization through Day 7 or hospital discharge (whichever occurs first). Serious adverse events will be recorded from randomization through the end of study (i.e., 180 day final follow-up visit, death, or withdrawal of consent).

In order to ensure prompt reporting of adverse events, we require that all adverse events (as well as all related study data) be entered into the REDCap web-based database (REDCap) within five working days of their becoming aware of the event during the initial admission. For all serious adverse events (SAEs), we require that they be reported in the REDCap within 24 hours of the study site staff first being made aware of the occurrence of the SAE. The 24-hour reporting requirement for SAEs applies to all study phases.

Reporting of serious or life-threatening adverse events will trigger notification of the event to the Medical Monitor (MM). The MM will conduct an independent review of these specific SAE. If the MM believes the adverse event is serious, unexpected and either definitely, probably, or possibly related to the investigational device(s) and/or study procedures, the TOC staff will forward a Safety Report (pre-filled with as much data as possible) to the clinical site Investigator to be completed with any additional information that may be relevant to the SAE. The Safety Reports will be included in the reports prepared for the DSMB. The principal investigator, at each clinical site, will be responsible for reporting to his/her own IRB/EC according to individual IRB/EC policies. After the submission of the initial Safety Report, the principal investigator at the corresponding clinical site will be responsible for obtaining follow-up information about the event, and reporting it to the TOC.

If it is determined that an unanticipated adverse device effect presents an unreasonable risk to subjects, the Principal Investigator will recommend the termination of all investigations or parts of investigations presenting that risk as soon as possible. The PI and SC shall make a determination regarding termination not later than 15 working days after the sponsor first receives notice of the effect. Termination of all investigations or the parts of investigations that have been deemed to present the risk(s) shall occur not later than 5 working days after the PI and SC makes this determination.

The trial will resume only after determining there is sufficient evidence to reinstate the trial, and after each clinical site obtains IRB/EC approval.

17. Ethical Considerations

The rights, safety and well-being of clinical investigation subjects shall be protected consistent with the ethical principles laid down in the Declaration of Helsinki. This shall be understood, observed and applied at every step in this clinical investigation.

It is expected that all parties will share in the responsibility for ethical conduct in accordance with their respective roles in the investigation. The Sponsor and the Investigator(s) shall avoid improper influence or inducement of the subject, monitor, the clinical investigator(s) or other parties participating in or contributing to the clinical investigation.

18. Protection of Patient Confidentiality

At all times throughout the clinical investigation, confidentiality will be observed by all parties involved. All data shall be secured against unauthorized access. Privacy and confidentiality of information about each subject shall be preserved in study reports and in any publication. Each subject participating in this study will be assigned a unique identifier.

The Investigator will maintain a confidential study subject list identifying all enrolled subjects. This list will contain

the assigned study subject's unique identifier and name. The Investigator bears responsibility for keeping this list confidential.

Monitors and auditors will have access to the study subject list and other information that personally identifies study subjects to ensure that data reported in the CRF corresponds to the person who signed the ICF and the information contained in the original source documents. Such personal identifying information may include, but is not limited to the subject's name, address, date of birth, and medical record number.

19. Ethics Committee/Institutional Review Board Approval

Institutional Review Board (IRB) / Ethics Committee (EC) approval is required prior to study commencement. The Investigator must also obtain renewal of IRB/EC approval as dictated by local requirements (but at least annually) during the entire duration of the study. The Investigator is responsible for fulfilling any conditions of approval imposed by the reviewing IRB/EC, such as regular reporting, study timing, etc. Study data required to be included in IRB/EC reports (e.g., Continuing Reviews) must be obtained from the SDMC; in order to ensure that accurate and consistent data are presented.

The Investigator will provide the Project Management (PM) team with copies of such approvals and reports. Withdrawal of IRB/EC approval must be reported to the PM team immediately following the investigator's knowledge of the withdrawal.

The reviewing Independent Review Board (IRB) / Ethics Committee (EC) must review and approve an Informed Consent Form (ICF) specific to this study. Prior to the start of the trial, the PM team will provide each study center with a sample ICF. The study center, to meet specific requirements, may modify this sample ICF; however, the ICF must contain all of the elements required by the protocol, regulations, and GCP. Each investigational site will submit a copy of their ICF to the TOC prior to submission to their IRB; and, the IRB/EC approved ICF and renewal approvals to the PM team as required for the duration of the study. The original, signed and dated ICF should be retained by the investigational site for monitoring, and a copy provided to the subject.

20. Informed consent

Upon confirmation of patient's eligibility, a written informed consent document must be obtained prior to any studyspecific evaluations being conducted. In accordance with US FDA regulations (21 CFR 50) and ICH-GCP Consolidated Guidelines (Federal Register, May 9, 1997, Vol. 62, Number 90), a witnessed, IRB-approved, informed consent will be required from all subjects or their legal representative (LAR) or family member, as defined in 21 CFR 50.3(m), prior to participating in this trial. At the initial contact with a potential candidate, the investigator(s) will provide an adequate explanation of the purpose, procedures, possible risks/benefits, and participant responsibilities; in addition to the fact that his/her participation is voluntary, that he/she may withdraw from the study at any time, and that the decision not to participate or to withdraw will not affect subject's care in any way. Potential participants or their legal representative or family member will be given ample opportunity to ask questions and to consider their decision. If the subject expresses a sustained interest, a signed and dated written informed consent will be obtained. A copy of the consent form will be given to the participant or their legal representative or family member, and another copy will be placed in his/her medical record. The informed consent must be obtained by either the clinical site PI or other members of the study team who have been delegated the authority to obtain informed consent. Each of the study team members with this delegation must be qualified in terms of education, experience, and training to obtain informed consent.

The written informed consent document (and any other written information to be provided to the study subject) should be updated whenever new information becomes available that may require significant revisions to the informed consent document previously signed by a subject. Any such revision or update must be approved by the reviewing IRB/EC before being provided to the study subject. Previously consented subjects will be made aware of the changes and depending on the extent and/or severity of the new information a subject may be asked to "re-

consent" to continued participation in the trial.

21. Quality Assurance

To ensure monitoring responsibilities are performed to the fullest extent possible on a real-time basis through the RedCap, an experienced clinical research group will perform on-site and centralized monitoring for the trial uploading of all source documents within the REDCap system. MSMC staff will manage the assignment of monitors to performance sites, the coordination of monitoring visits, and provide support to monitors while they are in the field. In addition to on-site monitoring, centralized monitoring (per the FDA's most recent monitoring guidance developed in August 2011) reflects a modern, risk-based approach. Centralized monitoring focuses on critical study parameters and relies on a combination of monitoring activities. In this recent guidance, the FDA has encouraged the implementation of centralized monitoring due to its ability to ensure quality and integrity of data. Centralized monitoring is also very effective at identifying data fraud, data fabrication, and data errors.

For the first subject enrolled at any site, 100% of the data will be verified to source documents. For subsequent subjects, a checklist of key outcome and safety data variables requiring source document verification (SDV) has been developed based on the trial's safety and efficacy endpoints. Source documents verifying each data point collected in the trial will be uploaded into REDCap for all study subjects. This will allow for data to be monitored in a real-time fashion and for any errors in data to be identified more quickly. A target of no less than 50% of the trial data submitted to the REDCap database will be verified against source documents from the performance sites prior to finalization of the database. Safety and efficacy variables represent approximately half of the data to be verified. The remaining half of source monitored data include: 100% of deaths and 100% of serious adverse events and all MSMC requested source data reviews based on the per-subject evaluation of safety parameters defined in the protocol. All data monitored are verified for accuracy and thoroughness using the most appropriate source documents for all subjects.

Signed informed consent documents and HIPAA are monitored for all subjects. Additional monitoring verification will include: ongoing evaluation of the adequacy of site facilities and staff, site recruitment, subject randomization, the presence of regulatory documents, and specific review of documents and data as requested by the MSMC staff. Each site will be monitored on a real-time basis through the uploading of all source documents into the REDCap system. Sites are evaluated in an ongoing manner by site monitors and MSMC staff to determine if there is a need to monitor more frequently or more thoroughly or via on-site evaluation.

Any omissions and corrections to data submitted to the database are noted and queries are generated by the monitor on site or immediately via REDCap's automated system. All queries will be stored in REDCap's logging and audit trail so that all data changes or questions regarding data accuracy are tracked and permanently recorded. The auditing trail will contain information regarding which monitor issued the query, which user was assigned the query at each site, the complete free text conversations discussing data questions and/or changes, and will provide time and date stamps for all query related processes.

Monitors will perform closeout-monitoring evaluations at the completion of subject enrollment. The monitor will again review all regulatory files and verify documents for accuracy and completeness as directed by the MSMC staff. Sites are instructed in the record retention of all trial documents. Principal Investigators are directed to close the trial and issue a final report to their IRB/EC following resolution of any and all outstanding issues at that site. Finally, any additional special considerations for the auditing of any additional safety issues will be made.

All documents and data shall be produced and maintained in such a way to assure control of documents and data to protect the subject's privacy as far as reasonably practicable. Only users with password-protected REDCap access will have the ability to view study data within the secure REDCap database. The Primary Investigator, Sponsor and representatives of regulatory authorities are permitted to inspect the study documents (e.g., study protocol, CRFs, and original study-relevant medical records/files) as needed. All attempts will be made to preserve subject confidentiality.

22. Protocol Deviations

A protocol deviation is defined as any study action taken by the clinical Investigator or site personnel in conflict with the Study Protocol. All protocol deviations will be entered into REDCap within 48 hours of the deviation. These will be tracked within the REDCap system and queries will be made and recorded as will through REDCap.

Deviations must be reported to the PM team regardless of whether medically justifiable, or taken to protect the subject in an emergency. Investigators will also adhere to procedures for reporting study deviations to their IRB/EC in accordance with their specific IRB/EC reporting policies and procedures.

Good Clinical Practice Guidelines require that Investigators maintain accurate, complete and current records, including documents showing the dates of and reasons for each deviation from the protocol.

23. Final Report

A final report will be completed, even if the study is prematurely terminated. At the conclusion of the trial, a multicenter abstract reporting the results will be prepared and may be presented at a major meeting(s). A multi-center publication may also be prepared for publication in a reputable scientific journal. The publication of results from any single center experience within the trial is not allowed until the aggregate study results have been published, unless there is written consent from the study PI.

24. Information Confidentiality

All information and data generated in association with this study will be held in strict confidence and remain the sole property of Principal Investigator. The Investigator agrees to use this information for the sole purpose of completing this study and for no other purpose without written consent from the Trial Operating Committee.

25. Trial Registration

The study will be registered in a publicly accessible trial database (e.g., clinicaltrials.gov) prior to study initiation.

26. Risk Analysis

A thorough risk analysis was performed as part of design control recommendations of the Quality System Regulation (21 CFR 820).

27. Publication Policy

Publication of the results of this trial will be governed by the policies and procedures developed by the Trial Operations Committee. The Publication Policy will be fully compliant with the voluntary NIH Public Access Policy mandated by the Consolidated Appropriations Act of 2008 (Division G, Title II, Section 218 of PL 110-161).

28. References

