5.8 Follow-Up Examination

5.8.1 Clinical

Several clinical outcome measures were selected for this study. These were chosen on the basis of their reliability, familiarity to the neurologic community, adaptability for use in patients who have had a stroke, and comparability to end points used in other trials of intracranial hemorrhage. All scores will be recorded in source documentation and entered into the electronic case report forms.

- 1. modified Rankin Scale (mRS, Appendix 4): mRS is an overall assessment of global handicap. In the original Rankin Scale, a score of zero indicates the absence of symptoms and a score of 5, severe disability. The modified Rankin Scale adds a score of 6 for fatal outcomes. A historical mRS will be obtained to assess the patient's level of function prior to the ICH. The score will be repeated as specified in Table 1.
- 2. The National Institutes of Health Stroke Scale (NIHSS, Appendix 5) is a 42-point scale that quantifies neurologic deficits in 11 categories. Normal function without neurologic deficit is given a score of zero. NIHSS should be done by a certified examiner as close to the specified times as possible.
- 3. EQ-5D-5L (Appendix 6) is a standardized instrument for use as a measure of health outcome. Applicable to a wide range of health conditions and treatments, the questionnaire provides a simple descriptive profile and a single index value for health status.

All day 7, discharge, day 30, day 90 and day 180 clinical outcome measures will be assessed by a qualified member of the research or clinical team either in person at a clinic visit, by phone or by mailed questionnaire. The schedule of neurological assessments is listed in Table 1. At each visit, the patient's medical record will be surveyed for any new or interim neurological adverse or serious adverse events. In addition, the patient or LAR will be asked about any interim neurological adverse or serious adverse events. The subject or LAR will also be specifically asked about any interim neurosurgical procedures.

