5.8.3 Serious Adverse Events

All serious adverse events occurring during the 180-days of study participation will be recorded. Adverse events and serious adverse events are critical endpoints and will be assessed as they occur and at the scheduled clinic visits. A serious adverse event is one that is fatal or life-threatening, is permanently or substantially disabling, requires or prolongs hospitalization, or any event that the treating clinician judges to be a significant hazard, contraindication, side effect, or precaution. For each recorded serious adverse event, the patient's attending physician will be asked to classify the causal relationship of the event to the study treatment as probable, possible, unlikely, and unrelated. Detailed form and narrative reports of the following specific adverse events will be obtained:

- Death (all cause) within 30 days of enrollment
- Death within 7 days of enrollment: Immediate peri-procedural death
- Symptomatic Re-Hemorrhage or New Hemorrhagic Event: any new intracranial hemorrhage or increase in size of pre-existing hemorrhage (IPH, IVH or extra-axial bleed) within 30 days associated with an increase of 4 or more points on the NIHSS or GCS increase ≥2 persisting for at least 24 hours and/or requiring emergency surgical decompression or resulting in death^{5, 6}.
- Symptomatic Evolution of Peri-hematomal Edema: Edema with increased mass effect or uncontrolled ICPs within 30 days requiring emergency surgical decompression NOT related to new or increased hemorrhage (i.e. edema related) associated with an increase of 4 or more points on the NIHSS or GCS increase ≥2 persisting for at least 24 hours, requiring emergency surgical decompression or resulting in death.
- Symptomatic Ischemic Stroke: A new ischemic stroke (ipsilateral, contralateral; contiguous with bleed/operative site or remote; cortical, subcortical or perforator distribution) within 30 days associated with an increase of 4 or more points on the NIHSS or GCS increase \geq 2 persisting for at least 24 hours, requiring emergency surgical decompression or resulting in death.
- Surgical complications related to Apollo /Artemis MIES: Surgical site infection, brain abscess or confirmed meningitis, or documented complication(s) deemed specifically related to the procedural anesthetic (medication, access or intubation related) within 30 days.

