7.5 Safety Analysis

7.5.1 Safety Outcomes

Several specific adverse events are monitored throughout the study. However the primary safety outcome to be assessed at completion of the trial will be death within 30 days.

The proportion of deaths for any reason through 30 days will be calculated and a 95% confidence interval will be presented. Survival estimates will be generated to evaluate the time-to-death using the Kaplan-Meier methodology for all deaths through 30 days.

All adverse events will be summarized by showing the number and percent of patients which report the event. Events will also be reported by relationship to the procedure or device.

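### The cut-off for recording non-serious adverse events (day 7 or discharge) does not exempt the listed 30-day surgical complications, so non-serious ones that occur later may go unrecorded

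*Combined protocol and SAP*

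**What the plan says.** **Cut-off for non-serious events.** Section 16.2: "Non-serious adverse events will be recorded from randomization through Day 7 or hospital discharge (whichever occurs first". Section 16 (Adverse Events) has the same rule: "Non-serious adverse events will be recorded from randomization through hospital discharge or 7 days whichever is earlier".

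**Serious events.** Section 16: "Serious adverse events will be recorded from randomization through the end of study (i.e., 180 day follow-up". Section 5.8.3 agrees: "All serious adverse events occurring during the 180-days of study participation will be recorded".

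**Listed events.** Section 5.8.3 asks for a detailed form and a narrative for a list of specific adverse events. The surgical item covers "Surgical site infection, brain abscess or confirmed meningitis" and "documented complication(s) deemed specifically related to the procedural anesthetic (medication, access or intubation related) within 30 days". Section 7.5.2.1 repeats the list as endpoints that the medical monitor assesses and that go into the safety reports for the EOC and DSMB.

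**Visits.** Under section 5.8.1 the medical record is, at each visit, "surveyed for any new or interim neurological adverse or serious adverse events". The patient or representative is asked the same, and is also asked about interim neurosurgical procedures. Table 1 marks an Adverse Events row from treatment through 6 months without separating serious from non-serious.

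**Analysis.** Section 7.5.1: "All adverse events will be summarized by showing the number and percent of patients which report the event". It gives no observation window for that summary.

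**The concern.** Two recording rules apply to the same event and give different answers. A surgical site infection managed without hospitalization, two weeks after the procedure, meets the 30-day definition in 5.8.3. Section 16.2 has by then closed recording of non-serious events. The protocol does not say which rule prevails.

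Safety data are part of the registry's primary objective, and section 2.1 names infection among the procedural risks. If sites resolve the conflict differently, the 30-day surgical-complication count mixes two ascertainment rules and can only err on the low side. A related gap concerns non-serious neurological events: 5.8.1 has sites look for them at every visit, while section 16 provides no recording of them after the cut-off.

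**Working it through.** The plan gives no figure for this point, so there is none to reproduce. The check compares the rules, then works out the windows and gives an illustration of scale.

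**1. Can a listed surgical complication be non-serious?** In 5.8.3 the re-hemorrhage, edema and ischemic stroke items carry thresholds: a change on the NIHSS or GCS that persists, emergency decompression, or death. The surgical item carries none. Section 16.1 defines seriousness by threat to life, hospitalization, significant disability, death, or medical judgment that the event may require intervention to prevent one of these. Brain abscess and meningitis would normally qualify. A superficial site infection treated as an outpatient, or a minor anesthetic complication, need not.

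**2. What happens to such an event on day 14, after discharge?**
- Under 16 and 16.2 it is outside the recording period for the Adverse Event CRF.
- Notification of the medical monitor in 16.2 is triggered by serious or life-threatening events, so this event has no stated trigger.
- Under 5.8.3 a form and narrative are due, because the event falls within 30 days. The same section has adverse events assessed as they occur and at scheduled visits.
- The prompts in 5.8.1 name neurological events and neurosurgical procedures, not the surgical site. Table 1 lists a focused exam at 1 month, but 5.8.1 lets follow-up outcomes be collected by phone or mail.

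**3. Windows.** Sections 16 and 16.2 count from randomization, which this single-arm registry does not have. I count from enrollment.
- Listed surgical complications, if non-serious and 16.2 governs: 30 − 7 = 23 days uncovered; 23/30 = 77%. Earlier discharge leaves more uncovered.
- Other non-serious events: 180 − 7 = 173 days uncovered; 173/180 = 96%.
- Serious events: 0 of 180 days uncovered.

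**4. Scale.** Maximum enrollment is 50 (Synopsis; section 4.5), so one missed event is 1/50 = 2 percentage points. At the 200 used in section 7.1 it would be 1/200 = 0.5 points.

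For illustration, assume N = 50 and a true 30-day complication rate r = 5%. That is the top of the under-5% estimate that section 2.1 gives for access-related bleeding, infection or damage; it is not an estimate for the listed item itself. Assume also a non-serious share s of 10% to 50% and a share l of 25% to 75% arising after the cut-off. The documents give neither share.
- Expected events: N × r = 50 × 0.05 = 2.5.
- Missed if 16.2 governs: N × r × s × l = 2.5 × 0.10 × 0.25 = 0.06, up to 2.5 × 0.50 × 0.75 = 0.94.
- Observed rate: r × (1 − s × l) = 0.05 × 0.975 = 4.9%, down to 0.05 × 0.625 = 3.1%.
- Chance of missing at least one: 1 − (1 − r × s × l)^50 = 1 − 0.99875^50 = 6%, up to 1 − 0.98125^50 = 61%.
- Missed if 5.8.3 governs: none of the listed events.

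**The case against.** The strongest reply is that 5.8.3 already covers these events. It is the specific rule, it has its own form-and-narrative route, it sits under the heading Serious Adverse Events, and 7.5.2.1 sends the same list to the medical monitor and the DSMB. Reading it as overriding the general cut-off is at least as natural as the reverse, and nothing listed is then lost. This stands as a possible reading, and it is why the conclusion is that events may be missed. It does not settle the matter: 16 and 16.2 state the cut-off twice without exception, the text that introduces the list speaks of specific adverse events and does not confine it to serious ones, and the notification trigger in 16.2 is limited to serious or life-threatening events.

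A reader might infer more than the documents support:
- **That late complications in general are undercounted.** They are not. Anything fatal, life-threatening, disabling, or requiring or prolonging hospitalization is serious and is recorded to day 180.
- **That Table 1 contradicts section 16.** Serious events are adverse events and are collected to 6 months, so the row is compatible with section 16. It lacks a footnote.
- **That a short window for non-serious events is itself an error.** It is a legitimate choice, stated consistently in both sections. Its dependence on length of stay matters for how the percentages are read, and disclosure is enough.

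**Conclusion.** The concern holds in a limited form. Sections 16 and 16.2 do not exempt the 5.8.3 events from the day-7-or-discharge cut-off, so a non-serious listed surgical complication after that point may or may not be recorded, depending on which section a site follows. The 30-day surgical-complication rate given to the DSMB may be understated. Thirty-day mortality and all serious events are unaffected.

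The size cannot be derived from the documents. Under the assumed inputs above, the expected loss is below one event in 50 patients if 16.2 governs, and zero among the listed events if 5.8.3 governs. The conclusion rests on two premises: that some listed complications are non-serious under 16.1, and that at least some sites would apply 16.2 as written. It should be fixed, because the count is a monitored safety measure in a small cohort and the repair is cheap.

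**What to change.** 1. In sections 16 and 16.2, state that the events specified in 5.8.3 are recorded on the Adverse Event CRF and sent to the medical monitor through day 30, whatever their seriousness.
2. Add surgical-site and procedure-related complications to the interim question at the 1-month visit, with the onset date. That visit has a window of ±14 days and can fall as early as day 16 (30 − 14), so the day-30 limit should be applied to the onset date. Where the visit is early, the remaining days should be checked at the next contact.
3. Reconcile 5.8.1 with section 16: say whether non-serious neurological events found at later visits are recorded.
4. Footnote the Adverse Events row of Table 1 to show which events are collected at which visits.
5. In 7.5.1, state the observation window for each adverse event table, and note that for other non-serious events it ends at day 7 or discharge and so varies with length of stay.

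The cost is protocol and CRF wording and one question at an existing visit. I would not require non-serious events to be followed to day 7 in patients discharged earlier: under 5.6.1 the discharge examination replaces the day-7 evaluation, so this would need a new contact or later recall.
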